2.3.2 Known Potential Benefits

Participating in this study provides genetic counseling and testing for free to participants. This is a service that is not always covered by insurance and could cost a significant amount out of pocket. Learning ones own genetic testing results may provide relief for some people. Additionally, depending on the results of genetic testing, some people may be eligible to participate in other clinical trials that aim to slow progression of disease, which some people may consider to be a benefit.

2.3.3 Assessment of Potential Risks and Benefits

The risk of causing significant depression, anxiety, or suicidality as a result of genetic counseling or testing are very low. Genetic counselors are trained to recognize unsafe conditions and changes in affect related to genetic testing. They will follow established clinical pathways and will alert the PI with concerns. Additionally, secondary outcomes include scales of depression, anxiety, distress, and suicidality, which will be monitored by the study team, overseen by the PI.

3 STUDY OBJECTIVES AND ENDPOINTS

Outcomes to be studied include cognitive and affective outcomes, which will be measured via questionnaire-based scales (See **Table 2**). The questionnaires will be administrated electronically utilizing REDCap, a secure online data collection tool. Outcome measures will be collected at multiple time points throughout the study; however, the primary outcomes include Genetics Knowledge Scale at 4 weeks after pre-testing counseling, Genetics Counseling Satisfaction Scale immediately after disclosure counseling, and the Revised Impact of Events Scale 3 months after genetic results disclosure. A data monitoring plan will be in place to ensure patient safety.

4 STUDY PLAN

4.1 Study Design

The proposed study is a single-center, prospective, factorial, non-inferiority, randomized cohort design to test the equivalence of telephone genetic counseling model to novel forms of pre-test genetic counseling and telegenetic results disclosure in participants with PD carrying a *GBA* or *LRRK2* variant (PD+*gene*+), participants with PD not carrying a *GBA* or *LRRK2* variant (PD+*gene*+), participants with PD not carrying a *GBA* or *LRRK2* variant (PD+*gene*-), and a group of at-risk *LRRK2* or *GBA* variant carriers without PD (PD-*gene*+). Participants will be recruited from a single center at the University of Pennsylvania Parkinson's Disease and Movement Disorders Center. A separate biobanking protocol, called the Molecular Inegration in Neurological Diagnosis MIND Cohort (UPenn IRB # 830237) enrolls subjects with PD and collects optional consent for recontact based on eligibility for additional studies. Subjects would be recruited to GET Virtual PD after enrolling MIND and after a blood or saliva sample has been collected and research-based genetic testing has been performed, but before clinical-confirmation genetic testing. GET Virtual PD will serve as the follow study to MIND that will allow access to genetic counseling and clinical genetic confirmation testing.

Enrolled participants will be randomized into one of 4 groups based on pre- and postgenetic test counseling: (1)IMAGINE-PD/Virtual, (2)IMAGINE-PD/Telephone, (3)Virtual/Virtual, and (4)Virtual/Telephone, stratified by genetic group. They will receive pretest genetic counseling through the Interactive Multimedia Approach to Genetic counseling to INform and Educate in Parkinson's Disease (IMAGINE-PD) website or via virtual visit with a genetic counselor. Participants will be asked to complete questionnaires on genetic knowledge, cognitive and affective outcomes prior to and 4 weeks after pre-test genetic counseling. All participants will then have clinical genetics results disclosure via virtual visit or by telephone with a genetic counselor. Patient-reported cognitive and affective outcomes will be measured 6 weeks and 6 months after genetic results disclosure. The hypothesis is that performance on the genetic knowledge scale and the revised impact of events scale will be equivalent between counseling groups at 4 weeks after pretest counseling and 6 weeks post disclosure, respectively.

4.2 Scientific Rationale for Study Design

Pretest counseling and post-test disclosure via IMAGINE-PD and telephone will be compared to virtual visits using an established telehealth video-conference platform to demonstrates equivalence between these remote telegenetic methods. Virtual visits were chosen as the comparator group because it is a remote model of genetic counseling that closely mimics in-person counseling, and randomized studies have demonstrated high patient satisfaction and favorable cognitive and affective outcomes with genetic counseling services delivered via video conferencing.¹² Although in-person counseling would be considered standard of care, both telephone and telegenetic counseling can be conducted remotely and are scalable to capture a larger number of people than in-person alone. We also felt that comparing in-person to telehealth or telephone would introduce bias because one group would be evaluated in their homes, while

Protocol 843748–	
GET VIRTUAL PD	
IMAGINE-PD	Page 18 of 41

the other would be conducted in the office, complicating the outcome measures. Finally, given the challenges presented by the current SARS CoV-2 Pandemic, remote models of telegenetic counseling are in even higher demand, and warrant comparison in a research study in this population.

4.3 End of Study Definition

A participant is considered to have completed the study if he or she has completed all phases of the study including the last visit or the last scheduled procedure shown in the Schedule of Activities (SoA), Appendix Section 12.1.

5 STUDY POPULATION

5.1 Inclusion Criteria

In order to be able to participate in this study, an individual must meet all of the following criteria:

- 1. Provision of signed and dated informed consent form
- 2. Stated willingness to have clinical confirmation genetic testing, and comply with all study procedures and availability for the duration of the study
- 3. Male or female, over the age of 21.
- 4. English Speaking

5.2 Exclusion Criteria

An individual who meets any of the following criteria will be excluded from participation in this study:

- 1. Prior genetic counseling and/or clinical testing specifically for Parkinson's disease
- 2. MoCA < 21, or a prior diagnosis of dementia during the screening phase

5.3 Screen Failures

Screen failures are defined as participants who consent to participate in the clinical trial but are not subsequently randomly assigned to the study intervention or entered in the study. A minimal set of screen failure information is required to ensure transparent reporting of screen failure participants, to meet the Consolidated Standards of Reporting Trials (CONSORT) publishing requirements and to respond to queries from regulatory authorities. Minimal information includes demography, screen failure details, eligibility criteria, and any serious adverse event (SAE).

5.4 Strategies for Recruitment and Retention

Potential participants are those PDMDC PD patients who have enrolled into the MIND study, had a blood or saliva sample collected, and have indicated that they would be willing to be contacted regarding their potential eligibility for additional studies (see IRB protocol 830237). These participants have all had research-based genetic testing, which is not disclosed to them because they were not conducted in a CLIA approved lab. A non-clinical research staff member will identify subjects with and without PD who carry a *GBA* or *LRRK2* variant from this database. A random sample of PD participants not carrying *GBA* or *LRRK2* variants will also be identified. These lists will be stripped of any genetic information and provided to the clinical research staff. The clinical research staff will initiate contact with potential participants and offer for them to be included in this research study. Subjects will be chosen at random from each of the lists by choosing 5 subjects per list to contact at a time. If a participant in MIND expressly states their interest learning their *LRRK2* or *GBA* status, they will also be invited to participate in

Page 20 of 41

this study at enrollment in MIND to be included in the next set of 5 subjects per list to be contacted.

We anticipate enrolling 3 subjects per week. Subjects will not be reimbursed for participating. To ensure enrollment of historically underrepresented groups, lists will include race and sex, and recruitment calls will ensure inclusion of women and non-white participants in each recruitment round. No vulnerable populations will be included in this study.

6 STUDY INTERVENTION

6.1 Study Intervention(s) Administration

6.1.1 Study Intervention Description

Virtual telemedicine and telephone genetic pretest and disclosure counseling: The virtual visits and telephone visits will be conducted by a certified genetic counselor to provide all counseling in accordance with guidelines set forth by the National Society of Genetic Counselors. The counseling visit will be conducted in real-time by telephone or via an established and secure audiovisual conferencing telemedicine platform (BlueJeans or Penn's approved telemedicine platform) within the PennChart/EPIC electronic medical record dashboard. See Genetic Counseling SOP for additional information.

IMAGINE-PD: The Interactive, Multimedia Approach to Genetic Counseling to INform and Educate in Parkinson's Disease (IMAGINE-PD) is a novel, interactive, web-based, audiovisual, self-guided, genetic counseling tool in the development phase through the UPenn Clinical Research Computing Unit (CRCU), which has expertise in research computing and development. Essential genetic counseling themes, outlined by a senior certified clinical genetics counselor in accordance with national guidelines, are presented in a web-based format, utilizing videos, text, pictures, and audio. The content was refined using a binned and tiered approach, previously described.¹³ User testing was conducted with PD patients and movement disorders physicians according to best practices.^{14,15} Feedback was incorporated and prototype was created. This version underwent usability testing according to NCI usability guidelines,¹⁵ and feedback was incorporated to create a final version. Participants can interact with IMAGINE-PD at their own pace, with the ability to move backward and forward, repeat sections, and have the ability to submit questions to the genetic counselor via e-mail. Web analytics will be provided by the CRCU.

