1.3 Schema

Study Schema: Overall Design.

Schedule of Events:

aute of Events.		
e -30-0 days S	Screening (Total n=385)	
• Screen potential participants by inclusion and exclusion criteria, call to invite to participate		
MoCA		
r 0 (Visit 1)	Randomization (N=80/group)	
IMAGINE-PD/Virtual, IMAGINE-PD/Telephone, Virtual/Virtual, Virtual/Telephone		
r 0 (Visit 1)	Baseline assessments/ Study Intervention	
Obtain informed consent, register in REDCap, train on BlueJeans platform, assign GUID		
• Pre-Counseling: Demographics, med history, medications, family history, GKS, GDS, STAI, PDQ-39		
Administer pre-test genetic counseling via IMAGINE-PD or virtual visit		
Observe saliva collection for genetic confirmation testing		
Post-Counseling: GCSS		
28-56 (Visit 2)	Genetics disclosure visit	
Pre-disclosure: GKS (primary outcome)		
Administer Post-test Genetic Counseling via virtual visit or telephone		
Post-disclosure: GCSS (primary outcome)		
Day 90-118 (Visit 3)Genetics disclosure follow up (3 months post-disclosure)		
28-56 (Visit 2) 0 Pre-disclosure: GKS (primary outcomession) 0 Administer Post-test Genetic Counce 0 Post-disclosure: GCSS (primary outcomession) 0	rome) seling via virtual visit or telephone utcome)	

Protocol 843748-
GET VIRTUAL PD
IMAGINE-PD

• IES-R, (Primary outcome), GCOS, GDS, STAI, PDQ-39, C-SSRS	
Day 210-238 (Visit 4)	End of study assessment (6 months post-disclosure)

• IES-R, GCOS, GDS, STAI, PDQ-39, C-SSRS

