2.3 Risk/Benefit Assessment

2.3.1 Known Potential Risks

This study provides genetic counseling and testing to all participants. The method of genetic counseling varies between randomization groups. There are no known risks that differ between forms of genetic counseling including web-based, telephone, or virtual visit methods. Potential risks of genetic counseling include anxiety, stress, or discomfort that can arise during genetic counseling. Genetic counseling during this study will be conducted by trained genetic counselors following clinical guidelines genetic counseling in PD. For participants randomized to IMAGINE-PD, participants will have access to a genetic counselor via email for any follow up or clarification questions. The risks of genetic testing are relevant to all participants, which include the potential for emotional, social, or financial consequences of the testing results. Some people may feel angry, sad, anxious, or guilty about the results. There is also a risk of genetic discrimination or of re-identification of deidentified genetic results.

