6.5 Study Intervention Compliance

The CRCU will provide web-analytics demonstrating time spent one each page, total time spent on the website, number of clicks, and times visited to the site. This information will be used to infer compliance with observing the pre-test counseling via IMAGINE-PD.

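### The plan does not close IMAGINE-PD or set closed-book conditions during the primary knowledge test, so one arm could answer with the teaching material open

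*Combined protocol and SAP*

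**What the plan says.** **The web arm.** Section 6.1.1 describes a self-guided website: "Participants can interact with IMAGINE-PD at their own pace, with the ability to move backward and forward, repeat sections". Section 6.5 says the analytics will include "total time spent on the website, number of clicks, and times visited to the site", and gives them one use: "This information will be used to infer compliance with observing the pre-test counseling via IMAGINE-PD". Section 2.3.1 adds that in this arm "participants will have access to a genetic counselor via email for any follow up or clarification questions".

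**The virtual arm.** Section 6.1.1: "The counseling visit will be conducted in real-time by telephone or via an established and secure audiovisual conferencing telemedicine platform". The only counselor document described is the summary letter in section 6.2. It follows disclosure, and so comes after the primary GKS.

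**Timing.** The Schedule of Events in section 1.3 puts both methods in the same Visit 1 slot: "Administer pre-test genetic counseling via IMAGINE-PD or virtual visit". The primary GKS is taken at Visit 2, Day 28-56, before disclosure (section 1.3 and the Schedule of Activities, 12.1).

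**Mode.** Section 3: "The questionnaires will be administrated electronically utilizing REDCap".

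**Hypothesis.** Section 9.1 expects GKS scores not to differ between IMAGINE-PD and virtual pre-test counseling, with a difference as the null.

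**Not stated anywhere in the text:** when site access ends, whether the GKS is observed or closed-book, and whether GKS results will be related to site use.

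**The concern.** The GKS is meant to show what participants know about four weeks after counseling. If one arm can open the teaching website while answering, its score mixes knowledge with look-up, and the virtual arm has no equivalent source described. The distortion runs one way, towards higher IMAGINE-PD scores.

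In a superiority comparison against an inferior tool, such a bias would blur the result. Here the aim is to show no difference, so a bias that covers an IMAGINE-PD deficit produces the result the trial hopes for. The practical risk is that a self-guided website is recommended as a substitute for a counselor on the strength of a score that partly reflects open-book answering.

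Section 4.2 already accepts this kind of argument: it rejects an in-person comparator because assessing the two groups in different settings would introduce bias. Test conditions for the GKS deserve the same care. The Schedule of Events specifies that saliva collection is observed, but sets no condition for the knowledge test. Once the data are collected, test conditions cannot be reconstructed.

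**Working it through.** **1. What the text establishes and what it leaves open**

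| Element | Established | Left open |
|---|---|---|
| Return to the site | Sections repeatable; visits counted (6.1.1, 6.5) | Whether access lasts until Visit 2 |
| Virtual arm material | Live session; letter only after disclosure (6.1.1, 6.2) | Content of the counseling SOP and attachments, not in the text |
| Test mode | Electronic, REDCap (section 3) | Whether staff observe it |
| Use of web log | Compliance only (6.5) | Whether it holds access dates |

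Nothing in the left-hand entries prevents look-up during the test. Nothing in the right-hand entries shows that it will occur.

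**2. The plan's own figure**

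Section 9.2, Table 3, gives 80 per group at a 0.5 SD limit, alpha 0.05, power 80%. Two one-sided tests (TOST) at 0.05 each, with a true difference of zero:

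n = 2 × (1.645 + 1.282)² / 0.5² = 68.5; 68.5 / 0.85 = 80.6.

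That reproduces 80 with 15% attrition. A two-sided difference test with 20% attrition also comes close (63 / 0.80 = 78.75, so 79). Either way the figure is for the IES-R. The plan gives the GKS no margin, SD or power, so what follows is an illustration.

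**3. Illustration of sensitivity to look-up**

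Assumptions, none of them stated for the GKS:
- Margin 0.5 SD, borrowed from the IES-R.
- True IMAGINE-PD deficit equal to the margin.
- TOST as the test.
- A mean look-up gain g across the whole IMAGINE-PD arm.

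Evaluable per level of the pre-test factor: 2 × 80 = 160, less 20% = 128. SE = √(2/128) = 0.125 SD.

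The chance of declaring equivalence is close to Φ(g/SE − z), with z = 1.645 at alpha 0.05 and z = 2.128 at 0.05/3. The second alpha applies Bonferroni across three primary endpoints.

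| Mean gain g (SD) | Apparent deficit (SD) | alpha 0.05 | alpha 0.05/3 |
|---|---|---|---|
| 0 | 0.50 | 5.0% | 1.7% |
| 0.10 | 0.40 | 19.9% | 9.2% |
| 0.20 | 0.30 | 48.2% | 29.9% |
| 0.25 | 0.25 | 63.9% | 44.9% |

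Example: g = 0.10 gives Φ(0.8 − 1.645) = Φ(−0.845) = 0.199.

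**4. How far the illustration moves**
- With 15% attrition (136 per level), the 0.10 SD row gives 20.6%.
- With margin and true deficit both at 0.75 SD, it is again 19.9%, because only g/SE matters.
- If the 0.10 SD arises from 10% of the arm gaining 1 SD, that arm's variance rises by 0.10 × 0.90 × 1² = 0.09. SE becomes √(2.09/128) = 0.128, and the result is Φ(0.783 − 1.645), about 19%.
- If IMAGINE-PD has no true deficit, look-up creates no false equivalence. It only tilts the estimate in that arm's favour.

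**The case against.** The strongest reply is that much of this is read from silence, and in several respects that is right.

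- **Open access up to the test.** A reader might infer that the site stays available until Visit 2. The text does not say so. IMAGINE-PD is scheduled at Visit 1, and the sentence on repeating sections may describe navigation within that sitting. Counting visits suggests that return is possible, but not that it continues to Day 28-56.
- **A virtual arm with nothing to consult.** This too might be inferred, but the documents show only that no pre-test material is described. The Genetic Counseling SOP, the Genetic Counseling Guideline and the attachments are not in the text. Both arms could also search the internet.
- **An unsupervised test.** Electronic completion at a remote visit does not establish that nobody is watching.
- **Fresher exposure as bias.** A participant who re-reads the site in week three has used the tool as designed. Under the ITT analysis of section 9.3, that gain is arguably part of the treatment effect. Only look-up during the test is clearly a measurement problem.
- **Size.** Sections 9.4.1 and 9.4.2 name two-tailed tests, linear regression and Bonferroni correction, not TOST. Section 8.1 says the GKS also covers attitudes and interest, which cannot be looked up, so any gain on the total would be diluted.

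What survives is narrower. The protocol sets no test conditions for a primary endpoint, and one arm's curriculum sits on a study website that allows repetition. None of the replies points to a safeguard in the text.

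**Conclusion.** The gap is real, and the direction of any bias is clear: look-up during the GKS would raise IMAGINE-PD scores and favour a finding of no difference. Whether it would occur, and its size, cannot be determined from the documents.

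The figure of about 20% (about 9% after Bonferroni) for a 0.10 SD gain rests on an assumed margin, deficit, gain and test. It shows that the conclusion is sensitive to a small gain. It does not estimate this trial's error rate, and the larger gains in the table should not be read as forecasts. The case for acting is that the change is cheap and can only be made before data are collected. Confidence is moderate.

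**What to change.** 1. In section 6.1.1 and the Visit 2 entry of the schedules, state that a participant's IMAGINE-PD access is suspended from the opening of the Visit 2 GKS until it is submitted. Say also whether access is otherwise open between Visits 1 and 2; re-reading in that period can remain part of the intervention.
2. Give both arms the same on-screen instruction to complete the GKS without materials or internet.
3. If the CRCU log can supply access dates, report the time from last access to GKS descriptively. Section 6.5 lists time per page, total time, clicks and visits, but no dates, so this needs confirming.
4. Do not rely on excluding recent site users. That would be a post-randomization exclusion in one arm only, of people who may differ in motivation or uncertainty. If it is run at all, label it exploratory.

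The cost is a short protocol amendment, an access setting and one line of instruction. The site is briefly unavailable during the Visit 2 questionnaire. A lock cannot stop other internet look-up; only the instruction to both arms addresses that.

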6.2 Genetic testing

All participants will have completed enrollment in the MIND protocol (UPenn IRB protocol #: 830237), and research-based *GBA* and *LRRK2* testing will be completed. A random selection of *GBA* or *LRRK2* variant carriers (gene+) and non-carriers (gene-) with PD (PD+), and a small sample of *GBA* or *LRRK2* variant carriers (gene+) without PD (PD-) will be selected by research staff not involved in clinical data collection. Gene+ groups will have variant confirmation testing in a CLIA-approved lab (outside vendor: Fulgent Genetics). Only the variant identified in research-based testing will be examined. No further testing will be conducted on this sample. For gene- groups research-based *GBA* and *LRRK2* mutation screening will be conducted in exactly the same manner as was previously performed. This will be conducted in collaboration with [name] [name] PhD at the University of Pennsylvania. This is not a CLIA approved test. Participants will be made aware of the possibility of having confirmation testing in a CLIA-approved lab or in a non-CLIA lab,

Protocol 843748-	
GET VIRTUAL PD	
IMAGINE-PD	Page 22 of 41

however, they will only learn which test was conducted at the disclosure visit to prevent partial unblinding of their results prior to confirmation testing and genetic counseling visit.

The results will be communicated to the patient via virtual visit or telephone, based on randomization. After the visit the genetic counselor will prepare a summary letter, including information specific to the results from that patient. This will be mailed to the patient. See Genetic Counseling Guideline for further description.

